4.4.3 Exploratory Efficacy Endpoints

4.4.3.1 FVC

Pulmonary function will be assessed by measuring forced expiratory vital capacity (FVC; ml). To adjust the FVC according to the height, the age and the gender of patients, the results of the FVC (in liters) will be divided by the theoretical capacity 'TC.' The change from baseline in the FVC/TC (as percent predicted for age and height) and the absolute value will be summarized at each visit using descriptive statistics. The FVC at each visit will also be summarized.

If height cannot be measured directly, ulnar length will be used to calculate a surrogate height measure as described in Section 4.3.1.

The TC is calculated from the following regression equations (Quanjer et al. 1993; Quanjer et al. 1995):

For patients from 3 to 17 years old:

$$\text{Female: } \ln(\text{TC}) = -1.4507 + (1.48 + 0.0127 * A) * H$$

$$\text{Male: } \ln(\text{TC}) = -1.2782 + (1.3731 + 0.0164 * A) * H$$

where H = height (m) and A = age (years) at the assessment visit.

For patients from 18 to 70 years old:

$$\text{Female: } \text{TC} = 4.43 * H - 0.026 * A - 2.89$$

$$\text{Male: } \text{TC} = 5.76 * H - 0.026 * A - 4.34$$

where H = height (m) and A = 25 if age is between 18 and 25 years, otherwise A = age (years) at the assessment visit.

If the height at a visit is missing, the last available measurement will be used to calculate the TC.

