## **2.6 EXPLORATORY OBJECTIVES**

The exploratory objectives for this study are as follows:

- To explore olesoxime treatment response of FVC in patients with SMA
- To evaluate the percentage of responders in patients with SMA, defined as patients who did not have a decrease from baseline in MFM scores
- To investigate the impact of SMN2 copy number *and other genes, transcripts, and proteins* involved in pathological pathways of SMA in patients with SMA on the safety, pharmacokinetics, pharmacodynamics, and efficacy of olesoxime
- To explore olesoxime treatment response to levels of SMN2 mRNA and SMN protein in blood
- To evaluate potential relationships between drug exposure, efficacy, and safety
- *To assess clinician-reported change in overall health status, as measured by the Clinical Global Impression of Change (CGI-C)*
- *To evaluate potential correlations between the collected sensor data from smartphone-based monitoring and MFM scores and to assess patients' adherence to smartphone-based monitoring*
- *To explore the potential effect of olesoxime on patient experience of fatigability, as measured by the clinician-reported Olesoxime Fatigability Survey (OFS)*

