4.3.1 Demographics

Summary statistics will be presented for the following demographic and baseline characteristics: age (at the time of first treatment in the open-label part of the study), sex, race, ethnicity, country, weight, height, body mass index (BMI) and tanner stage (for patients 9-17 years old).

If height cannot be measured directly (e.g. due to scoliosis or contractures) ulnar length will be used to calculate a surrogate height measure. For patients with an ulnar length measurement available and height indicated as 'derived' in the electronic case report form (eCRF), height will be derived from the measurement of ulnar length using the following formulae:

For patients 5-19 years old (Gauld et al. 2004):

$$\text{Female: height (cm)} = 4.459 * \text{ulnar length (cm)} + 1.315 * \text{age (years)} + 31.485$$

$$\text{Male: height (cm)} = 4.605 * \text{ulnar length (cm)} + 1.308 * \text{age (years)} + 28.003$$

For patients > 19 years old (Elia 2003):

$$\text{Female: height (cm)} = 95.6 + 2.77 * \text{ulnar length (cm)}$$

$$\text{Male: height (cm)} = 79.2 + 3.60 * \text{ulnar length (cm)}$$

Percentiles for weight-for-age, stature-for-age, weight-for-stature and BMI-for-age will also be presented for all patients. These will be based on the Centers for Disease Control and Prevention (CDC) growth standards. For patients > 20 years (240 months) old, percentiles will be based on the reference data for individuals 240 months of age. Percentiles for stature-for-age, weight-for-stature and BMI-for-age may be presented separately for patients whose height can be measured directly and those whose height cannot be measured directly.

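### Patients who turn 18 (or pass 19 with ulna-derived height) during follow-up change reference equation, which puts a step in change from baseline in FVC/TC with no change in FVC

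*SAP*

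**What the plan says.** Protocol 2.6 lists as an exploratory objective "To explore olesoxime treatment response of FVC in patients with SMA". SAP 4.4.3.1 divides FVC in litres by TC and states: "The change from baseline in the FVC/TC (as percent predicted for age and height) and the absolute value will be summarized at each visit". FVC itself is summarized at each visit, but the SAP does not mention its change from baseline.

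The first TC regression is headed "For patients from 3 to 17 years old" and is used with "where H = height (m) and A = age (years) at the assessment visit". A second regression applies from 18 to 70, with the age term set to 25 for patients aged 18 to 25.

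On height, SAP 4.4.3.1 says: "If height cannot be measured directly, ulnar length will be used to calculate a surrogate height measure as described in Section 4.3.1". In SAP 4.3.1, "height will be derived from the measurement of ulnar length using the following formulae", with one pair of formulas for ages 5-19 and another for ages above 19.

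Neither section says what happens when a patient's applicable equation changes between baseline and a later visit.

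**The concern.** A change from baseline in a ratio shows change in the numerator only if the denominator is built the same way at both times. Here the denominator can be built differently. A patient aged 17 at baseline and 18 at a later visit is divided by two different reference models. If height is ulna-derived, passing 19 also changes the height that enters TC. Any gap between the equations at the cut-off is recorded as a change in percent predicted.

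Crossings are to be expected. The larger parent study enrolled patients aged 3-25 for 24 months. Protocol 1.2.2 puts the time since last parent-study dose at 2.4-4.0 years at this study's baseline. That gives an approximate baseline age range of 3 + 2 + 2.4 = 7.4 to 25 + 2 + 4.0 = 31 years for those who completed. Follow-up may run to 4 years after the last enrolment (a fixed period of 3 years in the UK). Patients who enter at about 14 to 18 can therefore cross one or both cut-offs.

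At stake is whether a crosser's FVC/TC change can be read as a change in lung function.

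**Working it through.** The documents give no figure for this point, so there is none to reproduce. The check puts numbers into the SAP's own equations.

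**Inputs from the SAP** (H in metres, A in years, ulna u in cm)
- TC, 3-17 years: female ln(TC) = -1.4507 + (1.48 + 0.0127A)H; male ln(TC) = -1.2782 + (1.3731 + 0.0164A)H.
- TC, 18-70 years, with A = 25 at ages 18-25: female TC = 4.43H - 0.026A - 2.89; male TC = 5.76H - 0.026A - 4.34.
- Height in cm, 5-19 years: female 4.459u + 1.315A + 31.485; male 4.605u + 1.308A + 28.003.
- Height in cm, above 19 years: female 95.6 + 2.77u; male 79.2 + 3.60u.

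**Assumptions, not in the documents:** heights of 1.40-1.75 m, ulna lengths of 20-26 cm, and 50% predicted before the switch.

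**Method.** With FVC fixed, new percent predicted = old percent predicted x TC before / TC after. To isolate the switch from ordinary ageing, both equations are evaluated at the same age.

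**Switch at 18.0, same height.** Worked case, male 1.50 m:
- Younger regression: exp(-1.2782 + (1.3731 + 0.0164 x 18) x 1.50) = exp(1.22425) = 3.402 L.
- Older regression: 5.76 x 1.50 - 0.026 x 25 - 4.34 = 3.650 L.
- 50 x 3.402 / 3.650 = 46.6, a step of -3.4 points.

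| Build | TC before (L) | TC after (L) | Step (points) |
|---|---|---|---|
| Male 1.40 m | 2.879 | 3.074 | -3.2 |
| Male 1.50 m | 3.402 | 3.650 | -3.4 |
| Male 1.70 m | 4.749 | 4.802 | -0.6 |
| Male 1.75 m | 5.162 | 5.090 | +0.7 |
| Female 1.40 m | 2.563 | 2.662 | -1.9 |
| Female 1.55 m | 3.312 | 3.326 | -0.2 |
| Female 1.70 m | 4.280 | 3.991 | +3.6 |

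**Ulna switch at 19, same ulna, older TC regression on both sides.** Worked case, male 20 cm:
- Height before: 4.605 x 20 + 1.308 x 19 + 28.003 = 145.0 cm, so TC = 3.359 L.
- Height after: 79.2 + 3.60 x 20 = 151.2 cm, so TC = 3.719 L.
- 50 x 3.359 / 3.719 = 45.2, a step of -4.8 points.

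| Ulna | Height before (cm) | Height after (cm) | Step (points) |
|---|---|---|---|
| Male 20 cm | 145.0 | 151.2 | -4.8 |
| Male 22 cm | 154.2 | 158.4 | -3.0 |
| Male 26 cm | 172.6 | 172.8 | -0.1 |
| Female 20 cm | 145.6 | 151.0 | -3.8 |
| Female 23 cm | 159.0 | 159.3 | -0.2 |
| Female 26 cm | 172.4 | 167.6 | +2.7 |

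**Sensitivity.** The step is proportional to the starting percent predicted: for the male of 1.50 m it is -2.0 points at 30% and -4.8 at 70%. The SAP's age bands could also mean that the ulna switch falls at the 20th birthday. The steps for a 20 cm ulna are then -3.8 (male) and -2.8 (female) instead of -4.8 and -3.8.

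**The case against.** The strongest reply is that little turns on this. FVC is exploratory, no hypothesis is tested, and the SAP's natural-history comparisons cover MFM and medical complications but not FVC. FVC in litres, which neither switch touches, is shown at every visit. Some builds show almost no step, the sign is mixed in females, and the age-19 switch affects only ulna-derived heights. All of this stands and limits the weight of the point. The litre summary is only a partial safeguard: the SAP plans visit values rather than change, and litres are not adjusted for growth in a cohort that includes children.

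A reader might infer more than the documents support:

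- **Larger steps.** A male with a 22 cm ulna aged 17 at baseline and 20 later goes from 50% to 41.2%; a female with a 20 cm ulna goes to 42.1%. These totals include ordinary ageing. With one set of equations throughout (TC age held at 17, ulna age capped at 19) they would still fall to 47.9% and 47.8%, so about 2 points are not due to the switches.
- **A predictable group shift, or apparent decline in most crossers.** This needs the number of crossers and their sex and build. The documents give none of these, and opposite signs may partly cancel.
- **An artefact as large as true FVC decline.** The documents give no rate of FVC decline.
- **A bias against BID dosing.** Protocol 6.12 summarizes FVC change by dose at the time of assessment, and a patient's BID visits follow the QD visits, so crossings may cluster there. Without the number and build of crossers, neither size nor direction can be stated.

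**Conclusion.** The concern holds within limits. The SAP's own rules produce a deterministic within-patient step in change from baseline in FVC/TC when a patient passes 18, or passes 19 with ulna-derived height, and nothing in the plan handles it. At 50% predicted, the builds tried give -3.4 to +3.6 points at 18.0 and -4.8 to +2.7 points at 19, with near-zero cases at both cut-offs. These sizes rest on assumed heights, ulna lengths and percent predicted. That the step exists rests only on the SAP's equations and its use of age at the visit.

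The effect on any group mean cannot be computed from the documents. The point is worth correcting because FVC response is a stated objective and the correction is simple. It does not affect the primary safety objective or the MFM analyses.

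**What to change.** In SAP 4.4.3.1, for change from baseline in FVC/TC only:

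1. Keep each patient on the TC regression that applied at baseline, with the age term capped at the top of that regression's range. State whether age is in completed or decimal years.
2. Wherever height is ulna-derived, use one ulna formula per patient throughout, chosen by baseline age. Cap the age term at 19 for those on the 5-19 formula.
3. If height becomes unmeasurable after baseline, still allow ulna-derived height, using the formula for the patient's baseline age. Fixing the height method itself would leave such a patient without a usable height.
4. Keep the visit-level percent predicted as now defined.
5. Add change from baseline in FVC in litres.
6. Report how many patients cross each cut-off.

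Items 1 and 2 remove the equation-switch step by construction; only smooth ageing within one equation remains. For example, a male of 1.50 m with FVC 2.0 L goes from 59.5% at 17.5 years to 58.8% at 18.0 on the younger regression, if its age term is allowed to run to 18. The older regression gives 54.8% at 18.0.

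The cost is a few lines of SAP text and derivation code, with no new data. The small downside is that, for the change measure, young adults who entered as minors are referred to a late-adolescent reference. A patient who moves from measured to ulna-derived height still changes height method, which this rule does not remove.

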*Natural history studies in Type 2 and Type 3 SMA (Vuillerot *et al.* 2013; Mercuri *et al.* 2016) have shown that patients 6–15 years of age have a greater likelihood of substantial worsening of their condition within 12–24 months of the observation period, which is likely related to growth and weight gain without an increase in muscle strength. Thus, the 6–15 years age group may be appropriate for demonstrating maintenance of motor function. A post hoc analysis conducted in this age group showed a statistically significant separation of 3.61 points ( $p=0.036$ ) on the MFM D1+D2 scores at 24 months.*

A responder analysis was performed by comparing the MFM score at Month 24 with the score at baseline. Patients were considered responders if their motor function score did not worsen at Month 24 compared to baseline. A similar approach was used for the HFMS by comparing the score at Month 21 with the score at baseline. For the MFM total score, olesoxime treatment for 24 months resulted in a higher responder rate (56.3%) compared to placebo (38.6%,  $p = 0.0419$ ). When the analyses were performed on the HFMS score, the relative risk was 1.82 [95% CI: 1.16; 2.86] in favor of olesoxime ( $p = 0.0091$ ), with 28.1% responders in the placebo arm, compared to 49.5% in the olesoxime arm. *The pre-specified analysis of electromyography (CMAP / MUNE), FVC,*

PedsQL, and CGI were inconclusive. However, a post hoc responder analysis of the CGI using a responder definition, which mirrors the stable or improved MFM/HFMS responder, showed a statistically significant effect favoring olesoxime (relative risk of 1.23 [CI: 1.01, 1.49];  $p=0.0361$ ). For the patient-/parent-reported CGI, a similar pattern was identified, with a trend favoring olesoxime (relative risk of 1.19 [CI: 0.99, 1.44];  $p=0.0640$ ).

SMA-related complications were reported as adverse events in a lower proportion of patients in the olesoxime group compared with placebo. Most importantly, a lower proportion of patients treated with olesoxime reported severe lower respiratory infections. All other adverse events were equally distributed in nature and severity: 63 (38.2%) patients experienced at least one serious adverse event, with a lower rate in the olesoxime arm compared with placebo (34 [31.5%] patients vs. 29 [50.9%] patients).

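### When a visit has no height, carrying the last one into predicted lung capacity modestly overstates FVC percent predicted in patients still growing

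*SAP*

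**What the plan says.** SAP 4.4.3.1 defines the exploratory respiratory endpoint as change from baseline in FVC/TC, summarised descriptively at each visit. For ages 3 to 17, ln(TC) is minus "1.4507 + (1.48 + 0.0127 * A) * H" in girls and minus "1.2782 + (1.3731 + 0.0164 * A) * H" in boys, "where H = height (m) and A = age (years) at the assessment visit".

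Two rules cover an unavailable height. The first is: "If height cannot be measured directly, ulnar length will be used to calculate a surrogate height measure as described in Section 4.3.1". The second is: "If the height at a visit is missing, the last available measurement will be used to calculate the TC". The second therefore acts only when FVC was recorded and neither form of height was.

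Height is due at baseline and every 6 months (Protocol 4.4.4). Efficacy assessments are scheduled every 26 weeks (SAP 4.4). Unadjusted FVC is also summarised. The sensitivity analyses in SAP 4.4.4 concern the MFM only.

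**The concern.** Carry-forward suits a quantity that stays put, and a child's height does not. Because age advances while height is frozen, the rule updates one input to TC and not the other. In both child equations TC rises with height, so a stale, shorter height gives a denominator that is too small. Where height is rising, the error always favours apparent respiratory preservation, so it does not average out across such patients. The plan provides no flag, count or sensitivity analysis that would show how often this happens. At stake is the reading of FVC percent predicted over time among the younger patients.

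**Working it through.** The documents give no expected value or power for FVC, so there is no planned figure to reproduce. The check applies the SAP's own equations.

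**Inputs from the SAP.** The two child equations, with age taken at the visit.

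**Assumptions not in the documents.** FVC constant in litres, 60% predicted at the last measured height, and steady growth of 3-6 cm/year. The relative error does not depend on the first two. The error in points scales with the 60%, and the share hidden depends on FVC being constant.

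**Formulas.** Relative overstatement = exp(slope × growth since last height) − 1, where the slope is 1.3731 + 0.0164A (boys) or 1.48 + 0.0127A (girls). Share hidden = (carried − true) / (starting value − true). Differences below are taken before rounding.

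**One height missing, last height 26 weeks old**

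- Boy aged 10, 1.36 m. TC = exp(−1.2782 + 1.5371 × 1.36) = 2.253 L, so FVC = 0.6 × 2.253 = 1.352 L. At 10.5 years the slope is 1.5453.
  - Carried height 1.36 m: TC 2.278 L, 59.33% predicted, a change of −0.7.
  - True height 1.375 m (3 cm/year): TC 2.332 L, 57.98%, a change of −2.0. Error +1.36 points, 67% hidden.
  - True height 1.39 m (6 cm/year): TC 2.386 L, 56.65%, a change of −3.4. Error +2.69 points, 80% hidden.
- Girl aged 12, 1.50 m. TC = exp(−1.4507 + 1.6324 × 1.50) = 2.713 L. At 12.5 years:
  - Carried height: 59.43%.
  - True height 1.515 m: 57.99%. Error +1.44 points, 72% hidden.
  - True height 1.53 m: 56.58%. Error +2.85 points, 83% hidden.

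The part still visible comes from the age term.

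**Change from baseline at week 104, the actual endpoint.** Same boy, now aged 12:

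| Heights missing | 3 cm/year: true / carried / share hidden | 6 cm/year: true / carried / share hidden |
|---|---|---|
| Week 104 only | 52.2 / 53.5 / 16% | 47.5 / 49.8 / 18% |
| Last two | 52.2 / 54.7 / 32% | 47.5 / 52.2 / 38% |
| Last three | 52.2 / 56.0 / 49% | 47.5 / 54.7 / 58% |
| All since baseline | 52.2 / 57.4 / 66% | 47.5 / 57.4 / 79% |

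Across boys and girls with assumed starting ages of 6-14 years and growth of 2-8 cm/year, the four rows span 13-20%, 27-41%, 40-64% and 54-88%.

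**Cohort mean, illustration only.** Take the week 104 error of 2.3 points for one missing height, and assume 40-80% of patients are growing and 5-20% of their heights are missing. The shift is 2.3 × 0.40 × 0.05 = 0.05 to 2.3 × 0.80 × 0.20 = 0.4 points. Neither proportion is in the documents.

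**The case against.** The strongest reply is that the rule rarely acts and does little. It stands behind the ulna-derived height, height is due at the same visits as FVC, and a one-year-old height needs two consecutive failures. FVC/TC is exploratory, no hypothesis is tested, no natural-history comparison or age subgroup is planned for it, and raw FVC is shown alongside. Patients entered the parent trial at 3-25 years and reached this study's baseline 2.4-4.0 years after their last dose, so some will have finished growing. All of this stands and limits the importance of the point. Raw FVC is only a partial safeguard, because it does not adjust for the growth that FVC/TC is meant to capture.

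A reader might go further and infer that the rule hides most of the growth-driven decline. That is true of the fall since the last measured height. For change from baseline it requires no height since baseline, or about three consecutive missing heights at moderate to fast growth.

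A reader might also cite Protocol 1.2.2, where worsening at 6-15 years is described as something "which is likely related to growth and weight gain without an increase in muscle strength". That passage supports the choice of age group for showing maintenance of motor function. It makes no claim about FVC percent predicted, so applying it there is extrapolation.

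Finally, the sign of the error is certain only where recorded height would have risen. The SAP allows for scoliosis and contractures, and a patient may switch between measured and ulna-derived height, so recorded height need not rise steadily.

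**Conclusion.** The point holds as a minor, one-directional error in a fallback rule. In patients whose height is rising, each missed 26-week height overstates FVC percent predicted by about 1.4-2.9 points in the worked cases, given 60% predicted and growth of 3-6 cm/year. One isolated missing height hides about 13-20% of the week 104 change from baseline, and consecutive missing heights hide more. Patients who have stopped growing are unaffected. The documents do not give the rate of missing heights, so the effect on the cohort mean cannot be established; the illustration suggests tenths of a point at most. No primary or secondary analysis is touched. It is a cheap improvement.

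**What to change.** In SAP 4.4.3.1, for patients under 20 years, replace carry-forward by linear interpolation between the heights before and after the visit. Where no later height exists, set FVC/TC to missing at that visit; raw FVC is still summarised. Keep carry-forward for adults. Report, by visit, how many FVC/TC values rest on a substituted height.

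Holding a child on the last growth percentile is a tempting alternative, since SAP 4.3.1 already plans them: "Percentiles for weight-for-age, stature-for-age, weight-for-stature and BMI-for-age will also be presented for all patients". It would assume reference-population growth in children with SMA, which is debatable, so it is not recommended.

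The cost is a sentence or two in the SAP and a few lines of code, with no new data collection. A few FVC/TC values become interpolated or are lost, and percent predicted becomes slightly less favourable.

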4.4.3.2 MFM Responders

Responder rates, where a responder is defined as no worsening from baseline in the MFM D1+D2 score, will be summarized at each time-point. The following assumptions will be made in the calculation of responder rates:

- Patients without an MFM assessment at a visit will be classified as non-responders. If a patient performs the MFM-20 instead of the MFM-32 at any post-baseline visit the assessment will be set to missing.
- Missing individual items will be imputed to zero.
- Patients who withdraw prematurely (for any reason) will be classified as non-responders.
- Patients who die during the study will be classified as non-responders.

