## **3.2 END OF STUDY**

*The study will continue until olesoxime is commercially available in the patient's country, or as per local regulation, or per the Sponsor's decision to terminate the olesoxime*

program for SMA, but will not exceed 4 years after the last patient was enrolled in the study.

**NB** In the UK, the study will last for a fixed period of 3 years.

The end of this study is defined as the date when the last patient, last visit (LPLV) of the treatment period occurs.

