#### **4.4.17      Treatment Completion**

Patients will be asked to come for a final study visit as early as possible but not later than 6 weeks after the end of the study at the patient's site (as described in Section 3.2).

If a patient had a regular visit prior to up to 3 months before announcement of the study end the last regular visit will be regarded as the final visit. However, remaining IMP delivered to the patient should be returned to the trial site within 6 weeks of announcement of study end.

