### Schedule of Assessments (cont.)

Notes: All assessments should be performed within 14 days of the scheduled visit, unless otherwise specified. *Laboratory safety samples should preferably be collected first at each visit under fasting conditions.* Following food, the PRO assessments (in the pre-specified order) should be administered first. Then, all other assessment can be performed in the order convenient for the patient and site. *If it is not possible for the patient to perform all assessments during the day, the site may divide the assessments between 2 consecutive days.*

The following assessments may be performed by an HN professional: vital signs, urine pregnancy test, all lab assessments, and IMP dispensation.

- a Screening can be prolonged up to 6 weeks for relevant clinical, administrative, or operational reasons. Results of standard-of-care tests or examinations performed prior to obtaining informed consent and within 7 days prior to Day 1 may be used; such tests do not need to be repeated for screening.
- b *Dose increase visit can be performed either at next scheduled visit or at unscheduled visit (as described in Section 3.1.1.4).*
- c *Procedures should only be performed by patients that consent to Protocol BN29854, Version 4.*
- d Unscheduled visit: If the patient reports new or worsening of symptoms related to the disease or an adverse event, the treating physician can request that the patient come for a clinical visit for further assessment or monitoring. Assessments should be performed as clinically indicated.
- e The open-label treatment period can terminate at any time (please refer to End of Study Section 3.2). When the study is ended for a particular country, a completion visit should occur as soon as possible but no later than 6 weeks after study end. Patients who discontinue study drug prematurely will return to the clinic for a treatment discontinuation visit 28 ( $\pm 5$ ) days after the last dose of study drug. The assessments requested for Visit *N* represent the typical schedule of assessments during a scheduled visit.
- f Required follow-up information will be collected via a phone call. An unscheduled follow-up visit may occur if the treating investigator deems it necessary.

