2. STUDY DESIGN

Study BN29854 is a phase II, multicenter, open-label, single arm study to evaluate the long-term safety, tolerability and effectiveness of olesoxime (Roche No. RO7090919) 10mg/kg q.d. in patients with SMA who previously participated in one of the following two studies:

- Open-label phase Ib, dose-ranged, single and multiple dose study to assess safety and pharmacokinetics of olesoxime in 6-25 year old SMA patients (Trophos No. TRO19622CLEQ1115-1, Roche No. WP29845), and
- Phase II multicenter, randomized, adaptive, double-blind, placebo controlled study to assess safety and efficacy of olesoxime in 3-25 year old Type 2 or non-ambulatory Type 3 SMA patients (Trophos No. TRO19622CLEQ1275-1, Roche No. WN29836).

The study will consist of historical data collection, screening, treatment and safety follow-up periods. Patient visits will occur at 13, 26, 39 and 52 weeks and every 26 weeks thereafter for medical examinations, as well as safety and efficacy assessments. In addition, patients and their treating physicians will be requested to provide data for the period between the patients' last visit in the previous Trophos study and the screening period of study BN29854. Enrollment in the open-label treatment phase of the study is independent from the historical data collection, and a separate Informed Consent Form is required for each part. Patients (or their legal representatives) who do not consent to the historical data collection are still eligible to participate in the treatment phase of the study, and vice versa. The analysis methods that will be used for the historical data will be reported in a separate statistical analysis plan (SAP).

The study will continue until olesoxime is commercially available in the patient's country, or as per local regulation, or per the Sponsor's decision to terminate the olesoxime program for SMA, but will not exceed four years after the last patient was enrolled in the study. In the UK the study will last for a fixed period of three years after the last patient was enrolled.

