4. STATISTICAL METHODS

4.1 ANALYSIS POPULATIONS

4.1.1 Intent-to-Treat Population

The intent-to-treat (ITT) population will include all patients who received at least one dose of study medication and have at least one post-baseline assessment of MFM. The ITT population will be the primary population for efficacy analyses.

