4.4 EFFICACY ANALYSIS

As this is a single arm, open-label study no formal hypothesis testing will be performed. Data collected during the treatment phase of this study will be summarized using descriptive statistics and will be compared with observational data describing the natural history of the disease.

The baseline value will be defined as the last non-missing value recorded prior to or on the first day of the study drug (Study Day 1).

Post-baseline efficacy assessments (scheduled every 26 weeks), including assessments performed at an early discontinuation visit, will be assigned to a scheduled study visit based on the following time windows:

Visit	Study Day	Time Window (in Study Days)
V3 (Week 26)	183	Day 2 – Day 274
V5 (Week 52)	365	Day 275 – Day 456
V6 (Week 78)	547	Day 457 – Day 638
V7 (Week 104)	729	Day 639 – Day 820
V8 (Week 130)	911	Day 821 – Day 1002
V9 (Week 156)	1093	Day 1003 – Day 1184
V10 (Week 182)	1275	Day 1185 – Day 1366
V11 (Week 208)	1457	Day 1367 – Day 1548
...		

If multiple valid values for a variable are recorded in the same time window, the record closest to the scheduled study visit will be selected for summary of the data.

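### SAP 4.4.3.2 makes no exception for visits that never fell due, so read literally the MFM responder rate drops at late visits and interim cuts because of the calendar (minor)

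*SAP*

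**What the plan says.** - **The rule.** SAP 4.4.3.2 gives responder rates at each time-point and says: "Patients without an MFM assessment at a visit will be classified as non-responders". Premature withdrawal and death have their own bullets, both counted as non-response. The section names no denominator. SAP 4.1.1 says: "The ITT population will be the primary population for efficacy analyses".
- **Visit windows.** Under SAP 4.4, "Post-baseline efficacy assessments (scheduled every 26 weeks), including assessments performed at an early discontinuation visit" are assigned to visits by time window. The table runs through V9 (Days 1003–1184), V10 (1185–1366) and V11 (1367–1548), and is then left open.
- **End of follow-up.** SAP 2 ends the study at commercial availability in the patient's country, under local regulation, "or per the Sponsor's decision to terminate the olesoxime program for SMA", and at the latest four years after the last enrolment. Protocol Appendix 1, note e, adds: "The open-label treatment period can terminate at any time".
- **UK.** Protocol 3.2 says: "In the UK, the study will last for a fixed period of 3 years". SAP 2 says: "In the UK the study will last for a fixed period of three years after the last patient was enrolled".
- **Completion visit.** Protocol 4.4.17 asks for a final visit within 6 weeks of study end, but for a patient seen at a regular visit "up to 3 months before announcement of the study end the last regular visit will be regarded as the final visit". Appendix 1, note e, asks for a completion visit at country closure and states no such exemption.
- **Interim analyses.** SAP 2.3 and 4.8 allow them at unspecified times.

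No exemption for a visit that never fell due appears in SAP 4.4, 4.4.1.1, 4.4.3.2, 4.7 or 4.8, or in Protocol 6.12.

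**The concern.** A patient who completes because the study closed, or who is still on treatment at a data cut, has neither withdrawn prematurely nor died. Only the general missing-assessment rule catches that patient, and it counts a visit that could not have taken place as a failure.

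Mean change in MFM, by contrast, uses observed assessments only (SAP 4.4.1.1). At an exposed visit the responder rate could therefore fall while the mean change stays level. A reader could take the drop for loss of motor function when it only reflects when patients enrolled and when their country stopped.

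The exposed visits are those after an early sponsor or country stop, later UK visits, visits beyond V11, and late visits at an interim cut.

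**Working it through.** The plan states no expected responder rate and no calculation for this endpoint, so there is no figure to reproduce.

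**Step 1: direction.** Let p be the responder rate among patients who could be assessed, and u the share of ITT patients with no assessment because the visit never fell due. If the whole ITT population is the denominator:

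reported rate = p × (1 − u), understatement = p × u.

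The reported rate is below p whenever both p and u exceed zero.

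**Step 2: which visits are exposed.** Target day = 7 × week + 1, so V9 is Day 1093, V10 is Day 1275 and V11 is Day 1457.
- Four years is 4 × 365.25 = 1461 days. Taking first dose at enrolment, the last patient enrolled still reaches V11. If the study runs to its cap, u = 0 through V11 outside the UK.
- Three years is about 1096 days. If the protocol's UK wording means three years per patient, UK patients stop near V9, before the V10 window opens on Day 1185. Under the SAP wording, earlier UK enrollees can reach V10 and the last cannot.

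**Step 3: size, as illustration only.** The documents give neither the entry spread nor a stop date, so u is assumed. For p, take 56.3% from Protocol 1.2.2 (MFM total score, olesoxime arm, Month 24, earlier study). This is neither the D1+D2 score nor this study.

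| u | reported rate | understatement (points) |
|---|---|---|
| 10% | 0.563 × 0.90 = 50.7% | 5.6 |
| 25% | 0.563 × 0.75 = 42.2% | 14.1 |
| 50% | 0.563 × 0.50 = 28.1% | 28.1 |

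**Step 4: why the completion visit narrows the gap but does not close it.** Assume uniform entry over 365 days, a stop at Day 1095 for the last patient, announcement on the day of the stop, V9 on Day 1093, and 3 months = 91 days.
- With the exemption in Protocol 4.4.17, a patient below Day 1185 at the stop had V9 within the last 91 days and has no further visit. Then u at V10 = (1185 − 1095)/365 = 24.7%, and the reported rate is 42.4%.
- Under Appendix 1, note e, everyone has a completion visit. With a delay of d days, u = (90 − d)/365. For d uniform on 0 to 42 (mean 21), u = 69/365 = 18.9%, reported 45.7%. For d = 42, u = 48/365 = 13.2%, reported 48.9%.

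The same assumed stop gives u anywhere from about 13% to 25%, depending on which completion-visit text is followed and how quickly the visit happens.

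**The case against.** The strongest reply is that a visit means a visit that fell due. On the literal reading the bullets on withdrawal and death would seem redundant, since those patients have no later MFM anyway; the first bullet must then concern patients still in the study. That is a sensible intention, but the redundancy argument fails. SAP 4.4 assigns early-discontinuation assessments to visit windows, so a patient can withdraw and still have a score in a window. The withdrawal bullet is what makes that patient a non-responder.

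A second reply is that the whole-ITT denominator is inferred, and that Protocol 6.12 summarizes responders by dose at the time of assessment, which a patient without an assessment lacks. It is true that SAP 4.4.3.2 names no denominator. But the by-dose rule fits missed visits, withdrawals and deaths no better, and the SAP plainly counts those. It cannot be what removes only the visits that never fell due.

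A third reply is that little harm follows, and most of this stands. The endpoint is exploratory and untested. Completion and withdrawal are tabulated. The responder count does not depend on the denominator, so if the number assessed is shown, an observed-case rate can be recovered. ITT membership requires a post-baseline MFM, so patients with none at an interim cut are already excluded. The observed-case rate does not, however, separate visits missed from visits never due.

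A reader might also infer that about a quarter of patients would be miscounted at V10. The documents do not support that: the 24.7% rests on an assumed entry period and stop date and on one of two conflicting completion-visit texts.

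**Conclusion.** The concern holds as a minor point. SAP 4.4.3.2 states a rule with no exemption, follow-up is unequal by design, and interim cuts are allowed. Followed literally on the ITT population, the rule understates the responder rate at visits some patients could not reach, by p × u. The direction is certain under that reading. The size is not known, because u is not in the documents, and every percentage above is illustrative.

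Two stronger readings are not supported. One is that responder rates are understated throughout: visits that all patients reach are unaffected, including through V11 outside the UK if the study runs to its four-year cap. The other is that the main efficacy result is biased: MFM mean change uses observed assessments, and no hypothesis is tested. Nor is counting deaths, withdrawals and missed due visits as non-response at fault; only its extension to visits that never fell due is.

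**What to change.** Add one denominator sentence to SAP 4.4.3.2. At each visit, include the ITT patients who either have a valid MFM in that visit's window (SAP 4.4), or whose visit fell due (target day plus the allowed visit window) on or before their country's study end or the data cut. Within that set, keep deaths, premature withdrawals and missed due visits as non-response. Show the denominator at each visit and the observed-case rate alongside.

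The clause on valid scores is needed. A denominator based on the target day alone would, in the 12-month illustration, keep (1460 − 1275)/365 = 50.7% of ITT patients at V10, although 1 − 0.247 = 75.3% have a score in the window. With entry over 183 days it would keep only (1278 − 1275)/183 = 1.6%.

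Reconcile the UK study-end wording (Protocol 3.2 against SAP 2) and the completion-visit wording (Protocol 4.4.17 against Appendix 1, note e), because they determine which visits are due.

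The cost is one sentence, one flag and an extra table row per visit, plus the two reconciliations. The downside is smaller denominators at late visits. There is also a slight asymmetry: near closure, a completer with an early score is counted, while a patient who had already withdrawn and whose visit was not yet due is not. Showing how many were assessed but not due makes this visible.
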